### **2.3.3 Summary of Major Endpoints**

#### **2.3.3.1 Primary Endpoints:**

- Concentrations of TFV and FTC in blood serum
- Concentrations of TFV-DP and FTC-TP in PBMCs and CD4+ blood cells

### **2.3.3.2 Secondary Endpoints:**

- Concentrations of TFV, FTC, TFV-DP and FTC-TP in blood
- Concentrations of TFV and FTC in vaginal and rectal secretions
- Concentrations of TFV and FTC in vaginal/cervical and rectal tissue homogenates
- Concentrations of TFV-DP and FTC-TP in unselected and CD4+ vaginal/cervical and rectal tissue cells and tissue homogenates
- Concentrations of TFV, FTC, TFV-DP and FTC-TP in fluid (vaginal, rectal, semen), cells, and tissue homogenate
- Adverse experiences, including safety laboratory studies (hematological, renal, hepatic function)

### **2.3.4 Description of Study Population**

The study population will include approximately 32 evaluable (defined Section 7.3), generally healthy 18-44 year-old men and women, who are HIV-uninfected and not pregnant or breastfeeding. The upper age limit was selected to provide comparability in age for male participants with our pre-menopausal female participants and reduce the variability that might be introduced by a wider age range that could have a significant impact in this small study.

### **2.3.5 Trial Duration**

The total duration of participation from the Enrollment Visit to the Termination Visit is 7 weeks. Visits may be completed within specified windows around target dates. The approximate time to complete study enrollment is expected to be six months. The time of total study duration is expected to be approximately twelve months, including the study follow-up period. Detailed information regarding visit windows will be thoroughly described in the HPTN 066 Study Specific Procedures (SSP) Manual.

### **2.3.6 Expected Duration of Participation**

The expected duration of participation for enrolled participants approximately two months. No study data will be collected after the Day 49 final study visit.

## **3.0 STUDY POPULATION**

Thirty-two HIV-uninfected participants will be included in this study. Participants will be selected for the study according to the criteria in Section 3.1 and 3.2. They will be recruited as described in Section 3.3 and assigned to a study arm as described in Section 7.4. Issues related to

participant retention and withdrawal from the study, are described in Sections 3.4 and 3.5, respectively.

### 3.1 Inclusion Criteria

Participants who meet **all** of the following criteria are eligible for inclusion in this study:

- 18 to 44 years of age, inclusive on the date of screening.
- Provides informed consent for the study.
- Non-reactive HIV rapid test results at the screening and enrollment visits.
- An estimated calculated creatinine clearance (eCcr) at least 70 mL/min by the Cockcroft-Gault formula where:
  - eCcr (female) in mL/min =  $[(140 - \text{age in years}) \times (\text{weight in kg}) \times 0.85] / (72 \times \text{serum creatinine in mg/dL})$ .
  - eCcr (male) in mL/min =  $[(140 - \text{age in years}) \times (\text{weight in kg})] / (72 \times \text{serum creatinine in mg/dL})$ .
- Participants are sexually active, defined as at least one sex (vaginal or anal intercourse) act in the 30 days prior to screening.
- Participants must agree to use condoms for all coital events during study participation.
- Intensive sampling cohort only:
  - Not using spermicide as a means of birth control (in conjunction with a condom or diaphragm)
- Women must:
  - Be pre-menopausal
  - Have regular menstrual cycles with at least 21 days between menses (unless on contraception that causes amenorrhea or irregular menses)
  - Have a negative urine pregnancy test at screening and enrollment
  - Be utilizing an alternative method of birth control in addition to condoms (hormonal contraceptive, diaphragm or have undergone surgical sterilization) or have a vasectomized exclusive male partner.
  - Intensive sampling cohort only:
    - Have a cervix
    - Have documentation of a normal Pap smear within 12 months

### 3.2 Exclusion Criteria

- At screening:
  - Alanine aminotransferase (ALT) or aspartate aminotransferase (AST) greater than 1.5 X the site laboratory ULN (upper limit of normal)
  - Hemoglobin less than 10.0 g/dL
  - Platelet count less than 100,000/mm^3
  - Serum phosphate level below site laboratory LLN (lower limit of normal)
  - INR or aPTT greater than site laboratory ULN
  - Other safety tests (bicarbonate (HCO3), potassium (K), chloride (Cl), sodium (Na), calcium (Ca), fasting glucose) with results outside of the laboratories reference range
  - 1+ or greater protein on urine dipstick testing
  - 1+ or greater glucose on urine dipstick testing
- Culture-confirmed urinary tract infection
- Co-enrollment in any other HIV interventional research study (excluding behavioral only interventions) or prior enrollment in the active arm of a HIV vaccine trial.
- Clinically apparent or patient report of active skin disorders including: rash, pruritus, maculopapular rash, urticaria, vesiculobullous rash, and pustular rash.
- Women who are pregnant or breastfeeding.
- One or more reactive HIV rapid test results at screening or enrollment, even if HIV infection is not confirmed.
- Positive hepatitis B surface antigen (HBsAg) test.
- Excessive use of alcohol (more than 4 drinks a day on a regular basis).
- Interleukin therapy; medications with significant nephrotoxic potential, including but not limited to amphotericin B, aminoglycosides, cidofovir, foscarnet and systemic chemotherapy; and medications that may inhibit or compete for elimination via active renal tubular secretion (including but not limited to probenecid).
- Participants with a history of having a gastrectomy, colostomy, ileostomy, or any other procedure altering the gastrointestinal tract or drug absorption.
- Intensive sampling cohort only:
  - A positive test for syphilis, gonorrhea, or Chlamydia
  - A positive test for HSV-2 (individuals with active lesions only)
  - Findings consistent with bacterial vaginosis, vaginal candidiasis, or trichomonas (women only)
  - History of STI within 3 months prior to enrollment
  - Medications that prolong clotting time (e.g., warfarin, heparin, clopidogrel classes.)
  - Abnormalities of the colorectal mucosa, or significant colorectal symptom(s), which in the opinion of the clinician represents a contraindication to biopsy

(including but not limited to presence of any unresolved injury, infectious or inflammatory condition of the local mucosa, and presence of symptomatic external hemorrhoids).

- Clinically apparent pelvic exam finding (observed by study staff) of genital lesions, erythema, edema or any other abnormal physical or pelvic exam finding that, in the opinion of the investigator or designee, would contraindicate study participation.
- Women who have had cervical procedures (conization, LEEP procedure, cryosurgery) within the previous 6 months.
- Spermicide as a method for contraception within last 30 days
- Any other reason or condition that in the judgment of the investigator, would make participation in the study unsafe, complicate interpretation of study outcome data, or otherwise interfere with achieving the study objectives.

### **3.3 Recruitment Process**

Participants will be recruited from a variety of venues. Examples of such venues include local health clinics, local health departments, and family planning clinics. In order to reach a broader audience, college and local newspaper advertisements will be utilized. Fliers will be posted on frequently visited local venues. Electronic advertisement will include secure list-serves (university) and craigslist.com. All advertising materials must undergo approval by local IRB's.

### **3.4 Participant Retention**

Once a participant enrolls in this study, the study site will make every effort to retain him/her for 7 weeks of the study. Retention goal for the study is 95%. For each participant who is not fully evaluable (as defined in Section 7.3), an additional participant will be enrolled. Study site staff are responsible for developing and implementing local standard operating procedures (SOPs) to target this goal. Components of such procedures include:

- Thorough explanation of the study visit schedule and procedural requirements during the informed consent process and re-emphasis at each study visit.
- Thorough explanation of the importance of all study treatment groups to the overall success of the study.
- Collection of detailed locator information at the study Screening Visit, and active review and updating of this information at each subsequent visit.
- Use of appropriate and timely visit reminder mechanisms.

- Immediate and multifaceted follow-up on missed visits.
- Mobilization of trained outreach workers or “tracers” to complete in-person contact with participants at their homes and/or other community locations.

### **3.5 Participant Withdrawal**

Regardless of the participant retention methods just described, participants may voluntarily withdraw from the study for any reason at any time. The Investigator also may withdraw participants from the study in order to protect their safety and/or if they are unwilling or unable to comply with required study procedures after consultation with the Protocol Chair, DAIDS Medical Officer, SDMC Protocol Statistician, and CORE Protocol Specialist. Study visit and dosing requirements for research participant eligibility for safety and PK analyses is described in Section 7.2.

Participants also may be withdrawn if the study sponsor, government or regulatory authorities (Including the Office for Human Research Protections (OHRP) and FDA), or site IRBs/ECs terminate the study prior to its planned end date.

Every reasonable effort will be made to complete a final evaluation (as described in Section 5.5) of participants who terminate from the study prior to the final study visit, and study staff will record the reason(s) for all withdrawals from the study in participants’ study records.

## **4.0 STUDY TREATMENT/PRODUCT/INTERVENTION**

### **4.1 Study Product Formulation/Content/Storage**

The study product to be dosed in all treatment arms is Truvada® (FTC/TDF) tablet. Truvada® tablets are fixed dose combination tablets containing emtricitabine (FTC) 200 mg and tenofovir disoproxil fumarate (TDF) 300 mg in each tablet. Each bottle contains a silica gel desiccant canister that should remain in the original container to protect the study product from humidity.

#### **Study Product Storage**

FTC/TDF (Truvada®) study products should be stored at 25°C with excursions permitted to 15°C - 30°C (59°F-86°F).

## 4.2 Study Product Regimen(s)

Study participants who meet the inclusion/exclusion criteria (see Sections 3.1 and 3.2) will be randomized to one of four open-label treatment arms with emtricitabine (FTC) 200 mg/tenofovir disoproxil fumarate (TDF) 300 mg (Truvada®).

Table 4-1. Study Product Dosing Arms					
Treatment Arm	Study Product	Number of Tablets	Route	Frequency	Duration
1	FTC 200 mg/TDF 300mg	One(1)	Orally	Once Weekly	5 Weeks
2	FTC 200 mg/TDF 300mg	One(1)	Orally	Twice Weekly	5 Weeks
3	FTC 200 mg/TDF 300mg	Two(2)	Orally	Twice Weekly	5 Weeks
4	FTC 200 mg/TDF 300mg	One(1)	Orally	Once Daily	5 Weeks

## 4.3 Study Product Administration

FTC/TDF (Truvada®) tablets are administered orally with or without food.

### 4.3.1 Directly Observed Therapy (DOT) Guidelines

DOT is defined as directly observed therapy. A person identified by the Clinical Research Site (CRS) must observe and document the doses of study products taken by the study participant. Participants randomized to all arms will have all doses (as per randomized study arm) observed and documented.

The method by which DOT is to occur should be discussed at length with the participant at study screening. Participants and coordinators should formulate a well-described plan for DOT prior to entry. It is possible that participants may start coming to the clinic for DOT for the first few weeks and then switch to an alternate location as CRS study staff and alternative facilities permit.

Each CRS will be responsible for determining who can perform DOT for that site. The individual(s) could administer the study product or observe the study products being taken, depending upon his/her certification and legal requirements of the local jurisdiction. Someone who is not medically trained cannot offer advice about the study product.

The DOT observer must be an objective third party arranged by the CRS. Friends or family members are not permitted as observers. Individuals who might perform DOT include physicians, registered nurses, licensed practical nurses, physician's assistants, nursing assistants, certified home health aides, pharmacists, social workers, outreach workers, or other responsible individuals designated by the CRS.

DOT may be delivered in any location deemed appropriate by the CRS (i.e., in the home, clinic, pharmacy, or outreach center). The study staff are responsible for ensuring that confidentiality is maintained at the selected locations. Examples of clinic-based DOT used at sites include:

- Participant presenting daily to the site pharmacy for observed dosing by the site pharmacist who then documents on DOT participant log.
- Participant presenting daily to the entrance of the hospital/clinic and study coordinator bring participant's prepared study product to participant and study coordinator then documents on DOT participant log.
- Participant and study coordinator meet at a designated off-campus location (coffee shop) each morning for DOT and study coordinator documents on DOT participant log.

CRSs that plan to use off-site locations for DOT are advised to give careful consideration to the following issues:

- Confidentiality: Sites should consider where study paper work will be stored, how participants will be identified, how participant's prepared study product will be transported, and where participants will be observed. Confidentiality should be discussed with participants as plans for their DOT are developed. The participant should be comfortable with the person who will be observing DOT. Sites must also discuss confidentiality with the DOT observer, noting situations where breaches are most likely to occur. DOT observers may be required to sign a confidentiality agreement.

The place of DOT administration should be captured on the study treatment record. The primary location of DOT administration and any alternate or secondary locations of DOT administration should be documented in the participants' study files as well. A DOT log will be used as a primary source document to record date, time, place, study product administered or taken, observer signature, participant signature, and any intervention for missed DOT visit (i.e., telephone call).

Flexibility and creativity are needed as sites explore options for DOT delivery. It is recognized that sites will have some variability in the way they choose to administer DOT, but do need to report the delivery mechanisms they choose in the participants' study files. Sites will be asked to inform the study team of the methods they are considering before they are used. Sites that have questions should contact the HPTN 066 protocol team for guidance.

### **4.3.2 Follow-up for Missed Appointments**

Participants who miss a DOT visit must be contacted by the clinic. Sites can be flexible (e.g., some sites may choose to do a home visit if this is an available option while others may choose telephone contact). A tracking form has been developed for missed DOT visits as part of the study treatment record. Missed visits and reasons for missed visits must be recorded on the appropriate CRF.

### **4.3.3 Take-home Supply (for emergencies only)**

Take-home dosing may be provided to participants for emergency purposes. Additional details on the use of the emergency dose will be provided in the SSP manual.

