### 1.2.3 Dosing Duration Rationale

Dose-proportionality can be assessed at any point of observation following initiation of dosing. Intra-individual variability, however, can best be assessed at two sampling times not anticipated to vary based on PK principles. Essentially, by definition, this condition is achieved when steady-state has been reached. This study requires direct observation of dosing to rule out adherence as a cause for variation in drug concentrations. Therefore, we plan to begin sampling for intra-individual variability assessments as early as possible after dosing, balancing logistical difficulties (up to daily dosing for study staff and research participants) and PK limitations. Intracellular TFV-DP concentrations are estimated to achieve between 93% and 97% of steady-state Cmin (trough) concentrations after 4 half-lives and 5 half-lives, respectively, have elapsed after initiation of Truvada® dosing. Based on an estimated 150-hour TFV-DP intracellular half-life (FTC-TP will achieve steady-state earlier, given its far shorter 36-hour half-life), the 4 and 5 half-life points coincide with 28 and 35 days of dosing. Laboratory assay variation for all of the assays planned for this study are more than twice as large as the very small 4% difference in concentrations that we expect to measure between Day 28 and Day 35. Accordingly, we plan to dose for 35 days, and to use samples from Day 28 and Day 35 for our intra-individual variability estimates. One could argue for longer periods of dosing to further reduce differences between doses in the asymptomatic approach to a true steady-state, but we believe that our proposed plan provides a reasonable balance between logistical complexity (daily dosing under direct observation) and reasonable experimental variation.

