### **2.3 Study Design**

#### **2.3.1 Identification of Study Design**

HPTN 066 will be a Phase 1, multi-site, randomized, four-arm, open label study of the concentrations of TFV, FTC, and their metabolites in various body compartments following oral Truvada® dosing under direct observation by the site staff (directly observed therapy [DOT]) to assure 100% adherence to prescribed dosing regimen. The prescribed dosing regimens range from weekly to daily FTC/TDF at one of two possible doses. The overall study schedule and sample collection summary is provided in Appendix I. After participant education, informed consent, and screening for study eligibility, participants will have baseline procedures performed (e.g. phlebotomy) before the first dose.

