## 5.2 Enrollment Visit

Table 5-2. Enrollment Visit (Day 0)	
Component	Procedure/Analysis
Administrative	
 
• Review/update locator information
 
• Confirm behavioral eligibility, required for eligibility assessment
 
• Randomization
 
• Schedule next study visit
 
• Follow procedures for study arm assignment
 

Clinical	
 
• Update medical/menstrual history, required for eligibility assessment
 
• Update concomitant medications, required for eligibility assessment
 
• Review pre-existing conditions, required for eligibility assessment
 
• Perform physical exam (See Appendix IB), required for eligibility assessment
 
• *Refer for UTI/RTIs/STIs, treat or refer for other findings
 
• Provide counseling 
 
◦ Contraceptive
 
◦ HIV pre- and post-test
 
◦ HIV/STI risk reduction and condom
 
◦ Protocol adherence, product use/adherence
 
 
 
• Provide male condoms
 

Blood	
 
• HIV diagnostic testing (see SSP)
 
• Store plasma
 
• Collect PK blood specimens 
 
◦ Serum
 
◦ PBMCs
 
◦ CD4+ blood cells
 
 
 

Urine	
 
• Pregnancy testing (women only)
 

Study Product Supply	
 
• Administer first dose of study product
 
• Provide an emergency dose(s) of participant's prepared study product
 

\*If indicated (see SSP)

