### 5.3 Non-Intensive Sampling Visits

Table 5-3. Non-Intensive Sampling Visits (Days 1‡, 3‡, 7, 14, 21, 28, 35, and 49)	
Component	Procedure/Analysis
Administrative	
 
• Review/update locator information
 
• Schedule next study visit
 

Clinical	
 
• Collect interval medical/menstrual history
 
• Review/update concomitant medications
 
• Record/update adverse events
 
• Coagulation tests (Day 28 only, see SSP, intensive sampling cohort only)
 
• Perform directed physical exam
 
• Reinforce counseling 
 
◦ Contraception
 
◦ HIV/STI risk reduction and male condom
 
◦ Protocol adherence, product use/adherence
 
 
 
• Provide male condoms
 

Blood	
 
• Pre-dose #2: single blood draw for accumulation index (Day 1 for Treatment Arm 4, Day 3 for Treatment Arms 2 and 3, Day 7 for Treatment Arm 1)†
 
• Safety testing (Days 14, 28, 35 and 49 only, see SSP)
 
• Hepatitis B testing (Day 49 only, see SSP)
 
• Store plasma (Days 28 and 49 only)
 
• HIV testing (Day 49 only)
 
• Collect blood specimens for PK analysis 
 
◦ Serum
 
◦ PBMCs
 
◦ CD4+ blood cells
 
 
 

Urine	
 
• Collect urine sample (women only, Day 28 and 49 only) 
 
◦ Pregnancy testing
 
 
 

Study Product Supply	
 
• Administer study product (if applicable)
 
• Collect unused emergency dose of participant's prepared study product on Day 28 Visit for all arms. Provide a new emergency dose of participants' prepared study product on Day 28 Visit in Treatment Arms 2, 3, and 4.
 
• Collect unused emergency dose of participants' prepared study product on Day 31 Visit for treatment Arms 2 and 3, and on Day 34 Visit for Treatment Arm 4.
 

\* If indicated (see SSP)

† Sample collection for each cohort should be done no more than 1 hour prior to the second dose for each cohort. These will occur on day 7 (Cohort 1), Day 3 (Cohort 2 and 3), and Day 1 (Cohort 4), as indicated.

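### Take-home emergency doses conflict with the rule that every dose is observed, and a week-5 dose reported but not taken could distort the Day 28 v Day 35 variability estimate

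*Protocol*

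**What the plan says.** Section 4.3.1 is unqualified: "Participants randomized to all arms will have all doses (as per randomized study arm) observed and documented". Section 2.3.1 gives the purpose of direct observation as "to assure 100% adherence to prescribed dosing regimen", and Section 7.1 repeats it. Section 1.2.3 makes it a requirement of the variability objective: "This study requires direct observation of dosing to rule out adherence as a cause for variation in drug concentrations".

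Section 4.3.3 then states "Take-home dosing may be provided to participants for emergency purposes" and leaves the rules to another document: "Additional details on the use of the emergency dose will be provided in the SSP manual". The visit tables put this into effect. Table 5-2 (Day 0, all arms): "Provide an emergency dose(s) of participant's prepared study product". Table 5-3: "Provide a new emergency dose of participants' prepared study product on Day 28 Visit in Treatment Arms 2, 3, and 4". Unused doses are collected on Day 28 in all arms, then on Day 31 in Arms 2-3 and Day 34 in Arm 4.

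Sections 4.5.2 and 7.3 require week 4 and 5 doses to be taken on schedule, on pain of discontinuation. Neither says they must be observed. The definition of an evaluable participant in Section 7.3 and the primary analyses in Sections 7.6.1.1 and 7.6.1.2, which use all evaluable participants, do not mention emergency or unobserved doses.

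**The concern.** The two sets of statements cannot both stand. Either every dose is observed and there is no take-home supply, or there is a take-home supply and some doses may go unobserved.

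The timing gives this statistical weight. Intra-participant variability is the coefficient of variation of two samples, Day 28 and Day 35. The new supply issued on Day 28 covers the interval between them, and only in Arms 2-4. The enrollment supply is held until Day 28, so the Day 28 sample is open to the same question in every arm. A dose reported as taken at home but not taken would put adherence variation back into a quantity that the design is meant to free of it. Sections 1.1.6 and 1.2.1 intend that estimate for sizing later studies that use drug concentration as an adherence measure.

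**Working it through.** **Inputs.** Half-lives from Table 1-1: TFV-DP 150 h, FTC-TP 36 h. Twice-weekly dosing is Monday and Thursday (Figure 1-1 legend), so doses fall on Days 0, 3, 7, 10, ..., 28, 31. Arm 4 doses fall on Days 0 to 34. The Day 35 sample is pre-dose.

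**Reproducing the protocol's own figure.** R = 1/(1 − 2^(−τ/half-life)) gives 9.53 (daily) and 1.85 (weekly) for TFV-DP, and 2.70 and 1.04 for FTC-TP. Table 1-1 has 9.5, 1.9, 2.7 and 1.0. The model is the protocol's own.

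**Effect of one untaken dose on the Day 35 trough.** By linear superposition, with instantaneous input, the share of the trough due to the dose on day d is 2^(−24(35−d)/half-life) divided by the sum of the same term over all scheduled doses.

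| Last dose before Day 35 | Analyte | Share = fall if not taken |
|---|---|---|
| Arms 2-3, Day 31 (96 h before) | TFV-DP | 0.6417/1.9987 = 32.1% |
| Arms 2-3, Day 31 | FTC-TP | 0.1575/0.2049 = 76.9% |
| Arm 4, Day 34 (24 h before) | TFV-DP | 0.8950/8.3503 = 10.7% |
| Arm 4, Day 34 | FTC-TP | 0.6300/1.7024 = 37.0% |

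In Arms 2-3, Day 31 is the only dose between the Day 28 visit and Day 35, so it is the one that the new supply can replace. In Arm 4 the supply could instead replace a dose on Days 29-33, where the fall is 6.2-9.6% for TFV-DP and 3.7-23.3% for FTC-TP.

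**Effect on one person's two-sample CV (Arms 2-3, no other noise).** For two values the CV is |a − b|/√2 divided by their mean.
- TFV-DP: Day 28 trough 1.949. Day 35 is 1.999 if the dose was taken (CV 1.8%) and 1.357 if not (CV 25%).
- FTC-TP: Day 28 trough 0.2049. Day 35 is 0.2049 if taken (CV 0%) and 0.0474 if not (CV 88%).

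**Effect on a pooled estimate.** The protocol gives no within-person CV, so I assume 15%, with a range of 10-20%. With one affected participant in 32, on the log scale, the pooled value is √(w² + (ln ratio)²/(2 × 32)).
- FTC-TP: ln(0.0474/0.2049) = −1.46, so √(0.0225 + 0.0334) = 24%. Starting from 10% it becomes 21%, and from 20% it becomes 27%.
- Averaging squared raw-scale CVs gives a little less: √(0.0225 + 0.8825²/32) = 22%.
- TFV-DP: ln(1.357/1.949) = −0.362, so 15% becomes about 16%.

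**Effect on the proportionality slope.** One participant shifts the slope by (x − x̄) × ln(1 − f)/Sxx, where x = ln(dose multiple 1, 2, 4, 7), x̄ = 1.006, Sxx = 17.10 for 32 participants, and f is the fall.
- Arm 3 (x − x̄ = 0.380): −0.009 for TFV-DP, −0.033 for FTC-TP.
- Arm 4 (x − x̄ = 0.940): −0.006 for TFV-DP, −0.025 for FTC-TP.

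The acceptance limits are 0.64 to 1.36. In simulation at a CV of 35% and 8 per arm, power is 81.9% with no untaken dose (Table 7-1: 81.1%). It is 75.4% with one untaken Arm 3 Day 31 dose for FTC-TP, and 81-82% with one untaken Arm 4 Day 34 dose.

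**The case against.** **The route to harm is narrow.** The doses modelled fall on the days when Table 5-3 takes the spare dose back. A participant who attends on Day 31 or Day 34 can be dosed under observation. Harm needs a missed visit, a dose not taken, and a report that it was. Section 4.3.2 requires contact and a CRF entry after a missed DOT visit, and a known departure in weeks 4-5 ends participation. Section 4.3.1 also allows observation in the home, and nowhere is an emergency dose expressly called unobserved. All of this stands and lowers the likelihood. It does not verify ingestion: collecting the spare shows only whether a tablet is gone, and Section 1.1.3 itself says pill counts do not document pill-taking.

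**Stronger readings that the protocol does not support.**
- A reader might infer that any unverified week-5 dose moves the trough by 11-77%. That range needs the last dose before Day 35 not to have been taken.
- A reader might infer that users of the emergency dose stay evaluable and are analysed as fully adherent, or that no analysis safeguard exists. The protocol text contains no such safeguard, but use of the dose is deferred to the SSP manual. Neither that manual nor any SAP is shown, so this cannot be asserted of the trial.
- A reader might set the 77% against the 4% difference expected between Days 28 and 35 in Section 1.2.3. That 4% is residual TFV-DP accumulation. It is not expected variability and does not apply to FTC-TP.
- A reader might infer that the proportionality conclusion is at risk. One participant shifts the slope by at most about 0.03.

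**Conclusion.** The contradiction is plain on the page and must be reconciled. Its statistical consequence is conditional and falls mainly on the variability objective. If the last dose before Day 35 was reported but not taken, the Day 35 trough falls by 32% (TFV-DP) and 77% (FTC-TP) in Arms 2-3, and by 11% and 37% in Arm 4. One such FTC-TP case in Arms 2-3 could raise a pooled within-person CV from an assumed 15% to about 22-24%, while TFV-DP would hardly move. A home dose taken on time has no effect.

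These figures rest on the Table 1-1 half-lives, linear superposition with instantaneous input, and Monday/Thursday dosing. How often emergency doses are used is not stated, so no expected bias can be given.

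**What to change.** 1. Reconcile Sections 4.3.1, 2.3.1, 1.2.3 and 7.1 with Section 4.3.3 and Tables 5-2 and 5-3.
2. State in Section 7.3 whether a participant with an unobserved dose in week 4 or 5 is evaluable, and hence whether the replacement rule in Section 7.4 applies.
3. Flag unobserved doses from the DOT log described in Section 4.3.1, which already records date, time, place and observer signature.
4. Repeat the Day 28/35 variability analysis without participants who had an unobserved dose in weeks 4-5. Do the same for Day 35 proportionality as a sensitivity analysis.
5. Report the percentage of doses observed in place of an assertion of 100% adherence.

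The cost is wording, one flag from data already collected, and two repeat analyses, possibly with a few participants fewer in each. Which dosing or supply rule should prevail is for the sponsor to decide.
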